5.1 Patient flow

The CONSORT flow diagram for the Patient flow will be developed, see Figure 5.1 below for a draft. Numbers that remain to be established: 1) Patients admitted to the hospital wards during study period, 2) Patients meeting the inclusion criteria, 3) Patients excluded and reasons why, 4) Patients dying during hospitalisation, 5) Patients dying during follow-up, 6) Patients lost to follow-up, 7) Patients in intention-to-treat analysis (ITT).

[figure not shown]

Figure 5.1 Participant flow diagram

5.2 Protocol deviations

Protocol deviations that we are aware of and could impact the analysis include:

- One patient randomised to control received intervention by a pharmacist for ethical reasons
- One patient randomized to intervention was wrongly excluded because due to discharge before the intervention could start

5.3 Demographic and Baseline Variables

See Table 5.1 for baseline characteristics collected for the study population. Most data, including photocopies/print of laboratory values, TILT (No; Tidlig Identifisering av Livstruende Tilstander, Eng; Early Identification of Life-threatening Conditions) form, medication chart and admission notes (including information on medical conditions), were collected before randomization to avoid information bias. MMS-score (mini-mental status), walking test results and health-related quality of life (HRQoL) measurements was collected after study inclusion.

Table 5.1: Baseline characteristics of study population (n=xxx)

	Intervention group n=xxx	Control group n=xxx
Age, mean years		
Sex, F, n (%)		
Study Site, n (%)		
Tromsø		
Harstad		
Ability to self-provide consent, n (%)		
Marital status, n (%)		
Married		
Divorced		
Single		
Educational level, n (%)		
Elementary school		
High school (mandatory)		
Higher education (<4 years)		
Higher education (>4 years)		
Admitted from, n (%)		
Home		
Nursing home		
Other hospital		
Living status, n (%)		
Home		
Nursing home		
Handling medications themselves, n (%)		
Yes		
No		
Assistance from municipality to handle medications, n (%)		
Yes		
No		
Receiving medications as multidose packages, n (%)		
Yes		
No		
Co-morbidity (Mean score CCI)		
Number of medications in use at hospital admission/discharge, n (%)		
Total		

Regular use
Use as needed
MMS-score (n=??) (mean score)
Walking test results
Health-related quality of life (EQ5D-VAS
mean score)

CCI; Charlson Comorbidity Index, EQ5D-VAS; EuroQoL 5L - health-related quality of life, MMS; mini-mental status

5.4 Concurrent Illnesses and Medical Conditions

Comorbidities will be described applying the Charlson Comorbidity Index and potentially other comorbidity scores, e.g. Rx-Risk comorbidity index (3, 4). Comorbidities defined during hospital admission will be collected from admission and discharge notes. Information about ICD codes will also be achieved from the national registry (NPR) to ensure completeness in comorbidities.

5.5 Prior and Concurrent Medications

- Medications at admission is defined by information in the hospital admission letter and first medication chart provided
- Medications at discharge is defined by information in the hospital discharge letter

5.6 Treatment Compliance (intervention fidelity)

In our study, treatment compliance will be defined by describing which part of the intervention was performed by the pharmacists for which patient. We will also analyse the medication-related problems identified by the pharmacists, their recommendations and physician agreement and the recommendations. This is prospectively denoted in the study database.

6 Efficacy Analyses

6.1 General on statistics

We will investigate data for normality and apply the appropriate statistical tests. A two-sided 5% significance level will be applied, with no adjustments for multiplicity.

All analyses will be performed applying SPSS for windows or Mac. P-values < 0.05 will be regarded as statistically significant. P-values ≥ 0.001 will be reported to 3 decimal places; p-values less than 0.001 will be reported as "<0.001". The mean, standard deviation, and any other statistics other than quantiles, will be reported to one decimal place greater than the original data. Quantiles, such as median, or minimum and maximum will use the same number of decimal places as the original data. Estimated parameters, not on the same scale as raw observations (e.g. regression coefficients) will be reported to 3 significant figures.

6.2 Intention to treat and per protocol analysis

The main analysis will be performed according to the intention to treat (ITT) principle. In the ITT analysis all patients are analysed according to their initially assigned study arm at baseline, regardless of adherence to study protocol. Patients who withdrew consent or patients with a protocol violation concerning eligibility are excluded from the ITT analysis. Patients lost to follow-up will likewise be excluded from the ITT analysis. Per protocol analysis will also be performed. All subjects from the ITT population without protocol violations and deviations regarding treatment will be included in the PP population. See Figure 6.1 for illustration of ITT and PP analyses.

[figure not shown]

Figure 6.1: Patient inclusion for intention-to-treat (ITT) and per protocol (PP) analysis

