3.2 Inclusion-Exclusion Criteria and General Study Population

Eligible patients were all patients aged ≥ 70 years admitted acutely to one of the study departments, independent of disease status, medication use, or whether they were able to consent.

Patients admitted to the intervention wards were included if they were willing to provide written informed consent during hospital stay (patient or next of kin).

Patients were excluded from the study if they met one of the following exclusion criteria:

- admitted to the study ward more than 72 hours before evaluation of eligibility
- moved to and discharged from other wards during the index stay
- unable to understand Norwegian (patient or next of kin)
- considered terminally ill or with a short life expectancy
- planned discharged on the inclusion day
- occupying a bed in a study ward but under the care of physicians from a non-study ward
- intervention from a study pharmacist considered necessary for ethical reasons (before randomization or in control group)

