4.2 Analysis Populations

Full Analysis Population: All patients included in the study and not withdrawing their consent, regardless of whether they were excluded after randomization.

Per Protocol Population: The full analysis population, except those who were excluded after randomisation.

Assigning patients to full analysis and per protocol population will be conducted before data on the primary endpoint is collected.

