4.4 Missing Data

We do not expect missing data for the primary endpoint as our national health registries are complete. When data is missing in independent variables, results will be presented with specified total number of patients contributing to each variable. In addition, for dependent and independent variables with more than 5% missing data, multiple imputation will be considered. Results of raw and imputed data will be presented.

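### The main analysis in SAP 6.2 is labelled ITT but drops randomised patients whom the Full Analysis Population in 4.2 keeps, and some of these exclusions can arise after randomisation

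*SAP*

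**What the plan says.** SAP 6.2 makes ITT the main analysis and opens with the usual principle: "In the ITT analysis all patients are analysed according to their initially assigned study arm at baseline, regardless of adherence to study protocol". It then narrows the set: "Patients who withdrew consent or patients with a protocol violation concerning eligibility are excluded from the ITT analysis". It adds: "Patients lost to follow-up will likewise be excluded from the ITT analysis".

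SAP 4.2 defines the Full Analysis Population differently: "All patients included in the study and not withdrawing their consent, regardless of whether they were excluded after randomization". There, patients excluded after randomisation leave only the per-protocol set. Section 4.2 also fixes the timing: "Assigning patients to full analysis and per protocol population will be conducted before data on the primary endpoint is collected".

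Two exclusion criteria in SAP 3.2 matter here. One is "moved to and discharged from other wards during the index stay". The other is "intervention from a study pharmacist considered necessary for ethical reasons (before randomization or in control group".

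SAP 5.2 lists two known deviations: a control who received a pharmacist's intervention on ethical grounds, and an intervention patient wrongly excluded because discharge came before the intervention could start. SAP 3.3 says that care could not be blinded. On completeness, SAP 4.4 says: "We do not expect missing data for the primary endpoint as our national health registries are complete".

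**The concern.** A patient excluded after randomisation for an eligibility reason is inside the 4.2 population and outside the 6.2 ITT set. Section 6.2 does not mention the Full Analysis Population, and neither section says which definition prevails.

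This would be minor if eligibility were wholly a baseline matter. It is not. Under 3.1, randomisation follows confirmed eligibility and consent on the study ward, so a transfer and discharge from another ward is established only later, in either arm. Once patients are randomised, the ethical criterion can be met only by controls, and on the judgement of unblinded staff. If such cases count as eligibility violations, the main comparison loses patients for reasons that arise after allocation and partly depend on the arm. At stake is the protection against selection that the ITT label promises.

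**Working it through.** **The definitions side by side**

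| Patient | Full Analysis Population (4.2) | ITT (6.2) | Per protocol (4.2) | Per protocol (6.2) |
|---|---|---|---|---|
| Withdrew consent | out | out | out | out |
| Excluded after randomisation for an eligibility reason | in | out | out | out |
| Lost to follow-up | in | out | in, unless excluded after randomisation | out |
| Treatment deviation, not excluded | in | in | in | out |

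The sections agree on consent withdrawal, which is no part of the conflict. They disagree in the second and third rows on the main set, and in the third and fourth rows on the per-protocol set.

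**The two patients in 5.2**

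- The control is in the 4.2 Full Analysis Population. Under 6.2 this patient stays in ITT if the event is treated as non-adherence, and leaves if it is treated as the 3.2 exclusion criterion. The text allows both.
- The intervention patient is also in the 4.2 population. Under 6.2 the case looks like non-receipt of treatment, which would keep the patient in ITT, but the SAP does not say so.

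**Size of a possible bias**

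The SAP gives no figure for this. Inputs from SAP 3.4 are a control rate of 1.7 per year, a 16% reduction (ratio 0.84, so an intervention rate of 1.7 × 0.84 = 1.428) and a target of 250 per arm. The required total of 456 is not used. Assumptions: dropped controls have twice the average rate (3.4), and no intervention patient is dropped.

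With a share p of controls dropped, the remaining control rate is (1.7 − 3.4p) / (1 − p), and the observed ratio is 1.428 divided by that.

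- The one known control, p = 1/250 = 0.4%: (1.7 − 0.0136) / 0.996 = 1.693, and 1.428 / 1.693 = 0.843. The shift of about 0.0034 is about 2% of the 0.16 target effect.
- Hypothetical p = 2%: 1.632 / 0.98 = 1.665, ratio 0.8575.
- Hypothetical p = 5%: 1.53 / 0.95 = 1.611, ratio 0.887.
- Hypothetical p = 8%: 1.428 / 0.92 = 1.552, ratio 0.920.

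These shifts run towards no effect, that is, against the intervention.

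**False-positive risk when the true ratio is 1**

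Take 250 per arm, 1.7 events per patient (425 per arm), Poisson variance, and k controls dropped with m events each. The control rate becomes (425 − km) / (250 − k). With d = ln(ratio) / √(1/425 + 1/(425 − km)), the two-sided rejection probability is 1 − Φ(1.96 − d) + Φ(−1.96 − d).

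| k | m | Control rate | Ratio | Rejection |
|---|---|---|---|---|
| 1 | 6 | 1.683 | 1.010 | 5.3% |
| 5 | 6 | 1.612 | 1.054 | 11.8% |
| 10 | 4 | 1.604 | 1.060 | 13.1% |
| 10 | 6 | 1.521 | 1.118 | 34.5% |
| 10 | 1.7 | 1.700 | 1.000 | 5.0% |
| 10 | 0 | 1.771 | 0.960 | 9.1% |

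Dropping controls with the average rate does no harm. Dropping low-rate controls biases in the intervention's favour. Both size and direction depend on who is dropped, which the SAP does not reveal.

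**The case against.** The best defence is that little may follow in practice, and much of it stands.

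- A reader might infer that the plan fixes a control-only exclusion from ITT. It does not. Section 6.2 never names the case, 5.2 lists it as a deviation, and the principle of analysing patients whatever their adherence would keep that control in. The exclusion is one possible reading, obtained by combining 6.2 with 3.2.
- The ethical criterion is not purely a post-randomisation one. Its first limb applies before randomisation, and only the second raises the problem.
- A reader might suppose that the affected controls have the worst medication problems. The SAP does not say so, and the doubled rate used above is only an assumption.
- Only 6.2 designates a main analysis; 4.2 does not call its population the main set. Assignment before endpoint data are collected (4.2) and a statistician blinded to allocation (6.5) both limit a data-driven choice. They do not settle which definition applies. Moreover, loss during follow-up generally cannot be known until follow-up information arrives, which sits badly with the timing rule.
- With registry outcomes expected to be complete (4.4), the group lost to follow-up may be nearly empty. That makes the exclusion almost harmless, and also pointless.
- Figure 6.1 illustrates the ITT and per-protocol sets and might resolve the unclear cases. It was not visible in the text examined. It could not remove the conflict between the written definitions.

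**Conclusion.** The point holds as a defect of definition: 6.2 is wrong as written. It gives the name ITT to a set that drops randomised patients, contradicts 4.2, and can be read to admit exclusions arising after randomisation in an unblinded trial. The two per-protocol definitions also need to be reconciled.

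A large bias is not shown. On the one known control the shift is from 0.840 to about 0.843, given the assumed doubled rate and 250 per arm. The larger shifts rest on 2% to 8% of controls being dropped with no intervention patient lost. Nothing in the SAP supports those shares, and the ward-transfer criterion applies to both arms. Smallness is not guaranteed either: 5.2 covers only the deviations known to the authors, and 5.1 lists the counts of excluded patients and of patients in ITT as still to be established.

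**What to change.** 1. In 6.2, define the ITT set as the 4.2 Full Analysis Population: all randomised patients who did not withdraw consent, analysed as randomised.
2. State that ward transfer, a pharmacist's intervention in a control, discharge before the intervention and ineligibility found later affect only the per-protocol set.
3. Use one per-protocol definition in 4.2 and 6.2, and align Figure 6.1 with it.
4. State to which sets each of the two patients in 5.2 belongs.
5. Keep patients lost to follow-up in the analysis, with events and person-time up to the last observed date. The person-time formula in 6.3 subtracts only time in an endpoint and time after death from 365 days, so it needs a further term for censoring at loss.

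The cost is SAP wording and one added term in a formula. Outcomes come from national registries, so no new data source is needed. The downside is that a few ineligible patients may dilute the effect slightly; the per-protocol analysis can show whether this matters.

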6.3 Primary endpoint analysis

The composite endpoint

The primary endpoint is defined as the composite endpoint “acute readmission and ED visits” 12 months after discharge from the index hospital stay in the intervention group compared with the control group. Consequently, the endpoint comprises both “readmissions” and “visit to emergency departments (ED)”.

Hypothesis

- The H0 hypothesis is: The intervention does not influence the number of primary endpoints during 12 months after index hospitalization.
- The H1 hypothesis is: The intervention influences the number of primary endpoints during 12 months after index hospitalization.

Figure 6.2 illustrates how we assume that the endpoint will occur during the follow-up time.

[figure not shown]

Figure 6.2: Illustrations of primary endpoints during a 12-month follow-up time for patients in the two groups, assuming that we will see a difference between the groups.

- a) Number of patients having 1-x number of endpoints during the 12-month follow-up period.
- b) Cumulative number of endpoints (in total) 1-12 months after index hospital discharge.

Person-time (time under risk for experiencing an endpoint) contribution

Each patient may experience many endpoints during the 12-month follow-up, and the primary endpoint per patient will be related to the patient’s person-time contribution during the 12-month follow-up period after index hospital discharge.

To account for that a new endpoint cannot occur in the period a patient is “in an endpoint” (i.e. time in hospital if patient is hospitalised), and that patients may die before the end of the 12-month follow-up period, we will calculate person-time contribution for all patients, which is “time outside hospital” in the follow-up period where the person is still alive. Consequently, total person time contribution per patient =

365 days follow-up time after hospital discharge, minus “time in an endpoint” minus time after (potential) death.

Primary endpoint analysis

Specification

According to our published protocol, the primary analysis will be a Poisson regression comparing the rate of the composite endpoint during 12 months after discharge between the two study groups. In this SAP, we specify that the primary endpoint will be investigated by comparing the rate of events (also recurring) happening in the intervention group and the control group during the 12-month follow-up period, taking into account the specific person-time contribution per patient (when the patients are at risk for experiencing an endpoint).

We will supplementarily perform a Poisson regression analysis if we need to adjust for crucial differences between the study groups. This we will not know before we have the data in house.

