2.1 Objectives

The primary objective is to investigate the effects of the intervention on rate of emergency medical visits (acute readmissions and visits to emergency departments (EDs)) 12 months after hospital discharge.

Secondary objectives include to investigate the effects on:

- Acute readmissions
- Length of index hospital stay
- Time to first readmission
- 30-day readmissions
- Mortality rate

Specification:

- Regarding the primary objective, “Rate of emergency medical visits” is referring to the number of emergency medical visits per patient included in the trial.
- Regarding the secondary objectives, some that are described in the original published protocol will not be described in this SAP, but in SAPs for follow-up studies (see section 2.3).

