3.4 Sample Size

No data on hospitalization rates or visits to ED exist from our hospital. Therefore, data from a similar study in Sweden was applied as basis for sample size calculations. Gillespie et al. found a 16% reduction in visits to the hospital. In 12 months, patients in the intervention group had on average 1.5 visits and the intervention group 1.7 visits (2). If we expect a rate of 1.7 acute hospital visits per year in our control group, we would need a total of 456 patients to show a 16% reduction in hospital visits with a significance level of 5% and a power of 80% (Poisson regression). To compensate for dropout, we aimed to include 250 patients in each study group.

4 General Considerations

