6.5 Blinding

The dataset will be prepared for analysis by the project administrators who are familiar with the study and the variables ([name], [name] and [name]).

The main analyses will be performed by a statistician (FS) blinded for group allocation and not involved in data collection, data punching or in preparing the data files for analyses. To maintain blinding and prevent bias, data analyses on the primary endpoint will be performed as follows: [name]/[name]/[name] prepare a data file including a new variable indicating whether patients are in the intervention group or in the control group. This new variable is blinded, and allocation code is stored safely and not provided to the statistician (FS). FS receives the dataset with the new code for the allocated group and carry out the primary analysis. When the statistical analysis is finalized, group allocation will be revealed by [name]/[name]/[name] with FS present.

7 Summary of Changes to the Protocol

Compared to the published protocol and the information denoted in www.clinicaltrials.gov, the following amendments have now been made in the SAP:

- 1) The calculation of a retrospective Charlston Comorbidity index on all participants and the potential use of this as a covariate in analysis.
- 2) In the subgroup analysis overview, we have added a comparison of outcomes of patients from the two study sites Tromsø and Harstad and the number and type of comorbidities at discharge.
- 3) The primary endpoint analysis may not necessarily be a Poisson Regression analysis, but a comparison of rates of endpoints experienced by intervention group patients vs. control group patients.

8 References

3. Charlson Comorbidity Index (CCI) [cited 2020 20.04]. Available from: <https://www.mdcalc.com/charlson-comorbidity-index-cci>.

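### The primary comparison of recurrent-event rates has no stated test or variance, and Poisson, the only model named, makes no allowance for visits clustering within patients

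*SAP*

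**What the plan says.** Section 2.2 counts every acute readmission and ED visit per patient over 12 months, and section 6.3 expects repeats: "Each patient may experience many endpoints during the 12-month follow-up".

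Section 6.3 then describes the primary analysis as "comparing the rate of events (also recurring) happening in the intervention group and the control group during the 12-month follow-up period", allowing for each patient's own time at risk. That time is 365 days less time spent in an endpoint and time after death. The section continues: "We will supplementarily perform a Poisson regression analysis", on condition that important differences between the arms call for adjustment, which the SAP says can be judged only once the data have arrived. Section 7 records the change from the protocol: "The primary endpoint analysis may not necessarily be a Poisson Regression analysis, but a comparison of rates of endpoints".

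The sample size in section 3.4 was computed "with a significance level of 5% and a power of 80% (Poisson regression"). Section 6.1 states "A two-sided 5% significance level will be applied" and otherwise promises only a check of normality and suitable tests.

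The rate has more than one definition. Section 2.1 says it "is referring to the number of emergency medical visits per patient included in the trial". The hypotheses in 6.3 refer to the number of endpoints. The person-time paragraph in 6.3 uses days alive and out of hospital as the denominator.

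**The concern.** Table 6.1 names a method for each secondary endpoint. The primary endpoint has an estimate to compare (a rate over person-time) but no stated way of attaching an error to it. The reader is left with Poisson, the only model the SAP names for this endpoint.

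A Poisson variance assumes that, given exposure, all patients in an arm share one event rate. The SAP's own design makes that hard to believe. Section 3.2 admits patients from age 70 whatever their disease or medication, on a geriatric and a general medicine ward. Section 4.3 lists age, comorbidity, earlier hospital visits and place of referral as subgroups, and expects some variables to influence the primary endpoint. If such factors shift the visit rate and are not in the model, counts vary more than Poisson allows.

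This is the trial's sole primary test. Too small a variance would declare a difference too often when there is none, and would overstate precision whatever the result. Leaving the variance open means that the choice is made after the data arrive.

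**Working it through.** **The plan's own figure.** Section 3.4 gives 456 patients in total for a 16% reduction from 1.7 visits per year, at 5% and 80% power. The standard Poisson formula per arm is (z_α + z_β)² × (1/λ₁ + 1/λ₂) / (ln RR)². With λ₁ = 1.7 and λ₂ = 1.7 × 0.84 = 1.428:

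(1.960 + 0.842)² × (0.588 + 0.700) / 0.0304 ≈ 333 per arm, or 666 in total.

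The other two-sided Poisson formulas tried gave 626 to 664, so 456 is not reproduced. That is a separate point. What matters here is that 456 lies below the plain Poisson requirement, so it cannot be read as containing an allowance for overdispersion.

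**Inputs.** From the SAP: two-sided 5% (6.1), control rate 1.7 per year (3.4), 250 per arm (3.4), 1:1 allocation (3.3), all events counted (2.2). Assumed, because the SAP is silent: the dispersion k, where variance = mean + k × mean². At a mean of 1.7, k = 0.25 means a variance of 1.7 + 0.25 × 2.89 = 2.42, and k = 1 means 1.7 + 2.89 = 4.59.

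**Type I error if a Poisson variance is used.** The variance-to-mean ratio is φ = 1 + 1.7k. The true standard error is √φ times the Poisson one. The rejection rate under no effect is therefore 2 × (1 − Φ(1.96/√φ)), and the Poisson interval is 1/√φ of the correct width.

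| k | φ | Type I error | Interval width relative to correct |
|---|---|---|---|
| 0 | 1.00 | 5.0% | 1.00 |
| 0.1 | 1.17 | 7.0% | 0.92 |
| 0.25 | 1.43 | 10.1% | 0.84 |
| 0.5 | 1.85 | 15.0% | 0.74 |
| 1 | 2.70 | 23.3% | 0.61 |
| 1.5 | 3.55 | 29.8% | 0.53 |

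**Simulation check.** 20,000 null trials per setting, 250 per arm, gamma variation between patients, and 12-month mortality of 0, 20% or 30% (assumed).

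| k | Poisson variance | Patient-level robust variance |
|---|---|---|
| 0 | 4.9–5.1% | 5.0–5.2% |
| 0.25 | 9.7–9.9% | 5.1–5.2% |
| 0.5 | 14.3–15.3% | 4.9–5.5% |
| 1 | 22.6–23.5% | 5.2–5.4% |
| 1.5 | 28.6–29.5% | 5.1–5.2% |

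Both columns test the same person-time rate ratio, so the variance is the source of the excess. The settings varied death. Hospital days, which 6.3 also removes from exposure, were not among them.

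**The case against.** A reader might infer that the SAP sums all events over summed person-time, tests the two rates as Poisson, and therefore has an interval that is too narrow and a type I error well above 5%. The text does not support that. Section 6.3 never says the rates are pooled. It relates each patient's endpoints to that patient's own person-time, which fits a patient-level comparison or a robust variance just as well. Poisson regression is only a conditional supplement, and section 6.1 leaves room for whatever test is suitable. A test that is not named has no known error rate.

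The size of the inflation also rests on a dispersion that the SAP does not give. At k = 0.1 the error is only 7%. And section 6.5 has the primary analysis run by a statistician blinded to allocation, which limits a result-driven choice of method.

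All of this stands, and it makes the claim conditional. It does not close the gap. A normality check and a general promise of suitable tests do not deal with clustered counts. Blinding to allocation does not fix the variance in advance, and following the only model named, with its usual variance, gives wrong error bars for any k above zero. The denominator mismatch can be read as loose wording, with 2.1 stressing that all visits count and 6.3 giving the working definition. It has no bearing on type I error and is secondary, but the rates differ if mortality or time in hospital differs between arms.

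**Conclusion.** The point holds in conditional form. The SAP counts recurrent events, fixes no test, variance or interval method for the primary comparison, and nowhere provides for overdispersion. If a Poisson variance is used, type I error exceeds 5% for any positive dispersion: about 7% to 23% for k from 0.1 to 1 at 1.7 visits per year, reaching 10% at k of about 0.25. These figures depend on the assumed k and on the planning rate. The direction does not depend on the particular k, provided it is positive. That the trial's actual analysis was anticonservative cannot be concluded from this document.

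This is more than missing detail, because it concerns the sole primary test and the only named model would lead to the wrong variance. It should be corrected before the analysis.

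**What to change.** In sections 6.3 and 7, name before unblinding one primary analysis: regression of the event count on treatment with log(person-time as defined in 6.3) as offset, using either Poisson regression with patient-level robust variance or negative binomial regression. Choose one and state it. Report the rate ratio with its 95% CI. Any supplementary adjusted Poisson model should use the same robust variance.

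Reword the rate in 2.1 and the hypotheses in 6.3 to the same person-time rate, and give the ratio of per-patient counts as a sensitivity analysis.

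The cost is SAP wording; generalized linear models in SPSS, the SAP's stated software, fit either option. The interval will be wider but valid. It will also show how little power there is. For the planned 16% reduction with 250 per arm, power is Φ(|ln 0.84|/SE − 1.96), with SE² = (1 + 1.7k)/(250 × 1.7) + (1 + 1.428k)/(250 × 1.428). That gives 68% at k = 0, 54% at k = 0.25, 45% at k = 0.5 and 33% at k = 1. The fix does not cause this loss; a Poisson variance would hide it.
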